1.2 SCHEMA

1.3 SCHEDULE OF ACTIVITIES

	Outcome assessed	Pre-screening (Pre-consent)	Enrollment	Enrollment Month 0±2	Month 6 Month 6±2	Month 12 Month 12±2	Unscheduled Visits
Clinic Eligibility		X					
Aim 2							
EMR data abstractions	Retention, viral non suppression		X	X	X	X	
Informed Consent (surveys)	NA		X				
Caregiver/adolescent surveys	Secondary outcomes		X		X	X	
HCW surveys	Health service & Implementation outcomes		X			X	
HCW implementation logs/surveys	Implementation outcomes						X
HCW implementation surveys, IDI /FGD (intervention sites only)	Implementation outcomes				X		
Facility surveys	Implementation outcomes		X			X	
Adolescent/caregiver satisfaction surveys (intervention only)	Implementation outcomes					X	
Adolescent FGDs	Implementation outcomes						
Randomization	NA	X					

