Program records: We will abstract ALHIV medical record data at baseline and regular intervals throughout the study. Data from all adolescents with at least 1 clinic record within the 12-month period prior to the first data abstraction date will be included. Data will be abstracted at the facility or at the office of the technical partner that supports the EMR system at the facility. The EMR system captures data on client anthropometric measures, demographics, HIV testing history, family members, clinical history, ART adherence data, laboratory data, CD4 count, transfers, and discontinuations. Routine viral load testing (done 6 months after ART initiation, then annually) will be abstracted from the EMR, if available, or NASCOP's laboratory database. If EMR data is unavailable, paper medical records will be abstracted using mobile REDCap which enables automatic upload of data to a secure, password-protected study server.

Adolescent behavioral surveys: Adolescent surveys will include questions on socio-demographics, health care use, stigma, sexual behavior, psychosocial support, mental health, personal health knowledge, HIV disclosure and medication adherence. Surveys will be administered every 6 months either in-person or over phone by a trained study staff. Survey visits will coincide with clinic visits as much as possible.

Caregiver behavioral surveys: Caregiver surveys will include questions on socio-demographics and family, caregiver roles, HIV disclosure, HIV care experience, disclosure, social support, mental health, HIV testing and awareness, personal health and HIV experience, HIV stigma, ART knowledge and adherence. Surveys will be administered every 12 months either in-person or over phone by a trained study staff. Survey visits will coincide with clinic visits as much as possible.

Data on health services and implementation outcomes will be collected as previously described (see section 6.2).

To track implementation, the following surveys will be conducted:

Facility surveys: Facility managers will complete baseline and annual facility surveys to understand baseline resource capacity to implement future interventions and modifiable and non-modifiable health system factors. Variables will include availability of youth-friendly services, management and referral systems, and differentiated care services available.

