2.1. Summary of primary and secondary outcomes

Table 1. Outcome definitions and assessment

Outcome	Indicator	Source	Timing
Primary outcome			
Retention in care	Missed visits: Not seen within 30 days of a scheduled visit.	EMR data (Visit Date, TCA)	All visits occurring during the 12-month period after the study enrollment visit*
Secondary outcomes			
Loss to follow-up	Not return to care within the 12 months study interval	EMR data (Visit Date, TCA)	All visits after the first study visit until event or end of follow-up at 12 months. Participants marked as 'transferred out' or 'died' will be censored.
Viral non-suppression	Having HIV viral load (VL) >1,000 copies/mL	NASCOP data, abstraction of paper records	All visits from enrollment to 12 months follow-up*
Receiving differentiated care	
 Long inter-visit interval Fast-track visit 	EMR data (TCA, Care Model)	All visits from enrollment to 12 months follow-up*
Adherence	Pill coverage estimated by days of dosing and inter-visit interval since last visit >80%	EMR data (Visit Date, next Visit Date, Duration)	All visits from enrollment to 12 months follow-up*

*time window up to 12 months + 30 days

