2.2.2. Secondary outcomes and assumptions

Viral suppression: An average of 50 AYA VL records per facility and a minimum of 12 facilities per arm would be sufficient to detect a change from 64% to 82%, assuming 80% power, an $\alpha=0.05$ and coefficient of variation of 0.10 (Table 2).

Table 1. Sample size calculation of number of facilities per arm for the ITT analysis of retention and viral suppression

AYA per facility	ICC	Estimated proportion in study arm									
		Control	Intervention								
		75%	85%	86%	87%	88%	89%	90%	91%	92%	93%
200	0.10		26	21	18	15	12	11	9	8	7
150			27	22	18	15	12	11	9	8	7
100			27	22	18	15	13	11	9	8	7
50			30	24	20	17	14	12	10	9	8
	0.15	75%	85%	86%	87%	88%	89%	90%	91%	92%	93%
200			39	31	26	21	18	15	13	11	10
150			39	32	26	22	18	16	13	12	10
100			40	32	26	22	19	16	14	12	10
50			42	34	28	23	20	17	14	12	11
		64%	80%	81%	82%	83%	84%	85%	86%	87%	88%
200	0.10		13	11	10	9	8	7	6	6	5
150			13	12	10	9	8	7	7	6	5
100			13	12	10	9	8	7	7	6	5
50			15	13	11	10	9	8	7	7	6
	0.15	64%	80%	81%	82%	83%	84%	85%	86%	87%	88%
200			19	17	15	13	12	10	9	8	8
150			19	17	15	13	12	10	9	8	8
100			19	17	15	13	12	11	10	9	8
50			20	18	16	14	12	11	10	9	8

ICC: intraclass correlation coefficient; sample size estimated by assuming study power of 80%, significance level of 0.05 and coefficient of variation of 0.10

Section 3. Study Data Analysis

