3.5. Analysis of secondary study outcomes

3.5.1. Loss to follow-up:

- Loss to follow-up will be defined as a participant missed a visit and did not return to care within the 12-month study period. The proportion of loss to follow-up during 12-month study interval (window up to 12 months +30 days) will be compared between study arms using Poisson regression with robust errors.
- Time to loss to follow-up will be compared between arms by survival curves, and death or transfers will be censored. The hazard of loss to follow-up will be compared between study arms using Cox proportional hazards regression.

3.5.2. Viral non-suppression:

- Viral non-suppression will be defined as having HIV viral loads (VL) >1,000 copies/mL. Each VL testing result will be classified as VL suppressed vs. unsuppressed. The proportion of viral non-suppression during follow-up will be compared between study arms using mixed-effects Poisson regression with random effects for facility and participant and robust standard errors.

3.5.3. Receiving differentiated care:

- Receiving differentiated care will be defined in two ways. One approach will evaluate the next visit appointment date (scheduled inter-visit interval) – visits scheduled for ≥ 3 months after visit will be considered as differentiated care, in comparison to monthly visits recommended for AYA in current guidelines. The second approach will use the variable ‘fast-track’ at each visit – ‘fast track’ visits are considered as a component of differentiated care. Two analyses will be conducted (one for long scheduled inter-visit interval and one for ‘fast track’), each will be compared between study arms using mixed-effects Poisson regression with random effects for facility and participant and robust standard errors.

3.5.4. Adherence:

- Adherence will be evaluated using the proportion of days of pill dosing over days of inter-visit interval. The level of adherence during the past inter-visit interval will be assessed at each visit. A proportion over 80% as good adherence. The dichotomized adherence will be compared between arms using mixed-effects Poisson regression with random effects for facility and participant and robust standard errors.

Table 5. Analysis of secondary study outcomes

Loss to follow-up				
	Overall	Control	Intervention	Intervention vs. control
	Count (proportion)			^a RR (95% CI) ^b HR (95% CI)
Event Person-year Cumulative incidence Incidence rate (per 100 person-years)				
Viral non-suppression				

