	Overall	Control	Intervention	Intervention vs. control
	Count (proportion) / Median (IQR)			^c RR (95% CI)
Per participant Number of viral load assays				
Over all participants Number of viral load assays Number of non-suppression results (%)				
Differentiated care: long-interval visits scheduled				
	Overall	Control	Intervention	Intervention vs. control
	Count (proportion) / Median (IQR)			^c RR (95% CI)
Per participant Number of scheduled visits				
Over all participants Number of scheduled visits Number of long-duration interval (%)				
Differentiated care: fast-track visits				
	Overall	Control	Intervention	Intervention vs. control

DiSC UH3 Statistical Analysis Plan (SAP)

	Count (proportion) / Median (IQR)			°RR (95% CI)
Per participant Number of visits with non-missing care model				
Over all participants Number of visits with non-missing care model Number of fast-track visits (%)				
Adherence				
	Overall	Control	Intervention	Intervention vs. control
	Count (proportion) / Median (IQR)			°RR (95% CI)
Per participant Number of intervals with good adherence				
Over all participants Number of intervals with good adherence Number of intervals with good adherence (%)				

^a Estimated by Poisson regression with robust errors

^b Estimated by Cox proportional hazards regression

^c Estimated by mixed-effects Poisson regression models with random effects for facility and participant and robust standard errors

*Models adjusted for any factors differing between arm with statistical significance at enrollment

Section 4. Missing data

While we will attempt to follow all participants at 12 months, we anticipate that EMR data and VL data may be incomplete for some participants might be a challenge due to participant loss to follow-up – either due to loss from care, or silent transfer to another facility. Due to the level of missingness we expect, we will not conduct any formal imputation.

Section 5. Safety monitoring

Adverse and severe adverse events, including social harms such as violence or breach of confidentiality, will be monitored as they arise, and unblinded results will be reviewed by the DSMB. The DSMB will make recommendations regarding any imbalances in safety outcomes.

SAE #	PTIDNO	Study arm	SAE description	Onset date	Duration (days / unresolved)	Onset since randomization (days)	Relatedness to study

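### Baseline viral load is not a prespecified covariate in the viral non-suppression model, which gives up precision in a valid secondary analysis

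*SAP*

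**What the plan says.** SAP 3.5.2 classifies each VL result against 1,000 copies/mL and specifies the model: "The proportion of viral non-suppression during follow-up will be compared between study arms using mixed-effects Poisson regression with random effects for facility and participant". The text names no covariate. The only route to one is the footnote to SAP Table 5: "Models adjusted for any factors differing between arm with statistical significance at enrollment". SAP Table 3, the baseline table, has no VL row.

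Prior VL is within reach. Protocol 8.1 says "We will abstract ALHIV medical record data at baseline and regular intervals throughout the study", and the EMR abstraction row of the Schedule of Activities (Protocol 1.3), marked at enrollment, serves "Retention, viral non suppression". The source has limits: "Routine viral load testing (done 6 months after ART initiation, then annually) will be abstracted from the EMR, if available, or NASCOP's laboratory database". No VL is drawn for the study.

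SAP Table 1 sets the outcome window as "All visits from enrollment to 12 months follow-up", whereas 3.5.2 speaks of follow-up. For size, SAP 2.2.2 states "An average of 50 AYA VL records per facility and a minimum of 12 facilities per arm" and that this "would be sufficient to detect a change from 64% to 82%, assuming 80% power". Protocol 4.1 balances the randomization by county only.

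**The concern.** A participant's last VL status is likely to predict the next one, and a clinic's past suppression is likely to predict its later suppression. With 12 clinics per arm, most of the uncertainty in the arm comparison lies between clinics, and a baseline term can remove part of it. A rule that waits for a significant baseline difference does not use this information in most realizations of the trial. It also leaves the final model to depend on a test that the SAP does not specify. At stake are power for a secondary outcome and protection against a chance difference between the arms at the start.

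**Working it through.** **Inputs.** Suppression 64% vs 82%, 50 VL records per clinic, 12 clinics per arm, alpha 0.05, clustering parameter 0.10 or 0.15 (SAP 2.2.2 and its table). Two-sided testing is assumed. The table heads the parameter ICC and its note calls it a coefficient of variation. Read as a coefficient of variation, 0.10 gives 4.5 to 5.5 clinics per arm, which does not match the table, so it is used here as an ICC. The baseline-to-follow-up correlation ρ is not in the documents. Values of 0.3, 0.5 and 0.7 are assumed.

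**1. The plan's own figure.** The sum of p(1−p) over arms is 0.2304 + 0.1476 = 0.378. Individuals per arm before clustering: (1.96 + 0.842)² × 0.378 / 0.18² = 91.6. Design effect: 1 + 49 × 0.10 = 5.9. Clinics per arm: 91.6 × 5.9 / 50 = 10.8, rounded up to 11. This matches the table, and the same formula matches 71 of its 72 viral-suppression cells. The plan's size therefore assumes no baseline adjustment.

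**2. Power with and without a clinic-level baseline term.** Variance of the arm difference = [ICC × 0.378 × (1 − ρ²) + (1 − ICC) × 0.378/50] / 12. Power is from the noncentral t with 22 df (21 when adjusted). At ICC 0.10 and ρ = 0: (0.0378 + 0.006804)/12 = 0.003717, SE 0.0610, 0.18/0.0610 = 2.95, power 80.6%. The between-clinic share is 0.0378/0.0446 = 85%. At ρ = 0.5: (0.02835 + 0.006804)/12 = 0.00293, SE 0.0541, power 88.7%.

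| ICC | unadjusted | ρ 0.3 | ρ 0.5 | ρ 0.7 |
|---|---|---|---|---|
| 0.10 | 80.6% | 83.4% | 88.7% | 95.7% |
| 0.15 | 66.0% | 69.5% | 76.7% | 88.5% |

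A second method uses the effective sample size (600/5.9 = 101.7 per arm) with normal quantiles and multiplies the whole variance by 1 − ρ². It gives 82.9%, then 86.3 / 92.0 / 98.4% at ICC 0.10. At ICC 0.15 it gives 68.4%, then 72.6 / 80.6 / 93.0%.

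**3. Sampling error in the baseline.** The formula in step 2 treats ρ as the correlation with an error-free clinic baseline. A cluster-level simulation (4,000 trials, ICC 0.10, measured baseline proportions) gave 84.8% to 89.1% at latent ρ 0.5, a gain of about 4 points. At latent ρ 0.7 it gave 84.4% to 94.2%, a gain of about 10.

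**4. What the footnote recovers.** A second simulation (3,000 trials per scenario, ICC 0.10) varied the clinic-level and individual-level latent correlations.

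| Strategy | Power |
|---|---|
| Never adjust | 82–84% |
| Adjust only if baseline differs significantly | 82–85% |
| Always adjust (0.3/0.3) | 85% |
| Always adjust (0.5/0.5) | 88% |
| Always adjust (0.7/0.5) | 96% |

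**5. Size of chance imbalance and of the trigger.** SD of the baseline arm difference = √(2 × [ICC × p(1−p) + (1 − ICC) × p(1−p)/50] / 12), at ICC 0.10. Protocol 9.2 builds its 64% as 85% suppressed times 75% in care. SAP 3.5.2 analyzes test results, so 85% is the closer figure for people with a VL on record.

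- Non-suppression 15%: √(2 × [0.01275 + 0.002295]/12) = 5.0 points. Chance of a gap over 5 points 32%, over 10 points 5%. A clustered test is significant beyond 1.96 × 5.0 = 9.8 points (10.4 with t, 22 df).
- Non-suppression 36%: √(2 × [0.02304 + 0.004147]/12) = 6.7 points. Chances 46% and 14%. Trigger 13.2 points (14.0 with t).

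If the baseline test ignored clustering, the trigger at 36% would be 1.96 × √(2 × 0.2304/600) = 5.4 points. The SAP does not say which test applies.

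**6. Validity.** Null rejection for the unadjusted test was 4.7–5.2% in the second simulation.

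**The case against.** The strongest reply is that the planned analysis is sound as it stands. The outcome is secondary, and the stated scenario reaches 80% power without a covariate. Clinics are randomized and the model has a facility random effect, so chance differences between clinics are already in the standard error. All of this stands.

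A reader might infer that baseline imbalance goes wholly uncorrected. The documents do not support that: the footnote covers any factor that differs significantly and is not expressly limited to Table 3 rows. A reader might also infer bias, with a baseline gap read as an intervention effect. Null rejection near 5% rules that out as a systematic problem. Nor is VL unique among the secondary outcomes in having a pre-trial value: Protocol 8.1 lists adherence data in the EMR, and Table 3 lists use of a differentiated care model.

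The gain is uncertain. It rests on an undocumented correlation, and both the formula and the simulations work on clinic proportions, not on the planned repeated-measures Poisson model. Baseline VL may be about a year old or absent, and SAP Section 4 plans no imputation. These points limit the size of the claim. They do not give a reason to leave the covariate to a significance test.

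**Conclusion.** The point holds as one of efficiency. Baseline VL is not prespecified, and the significance-triggered rule recovers almost none of what it could give. The gain at ICC 0.10 is roughly 2 to 15 power points for assumed clinic-level correlations of 0.3 to 0.7. The 8-point gain at 0.5 in the closed formula is too firm a figure, since allowing for a baseline measured with error brings it to about 4. At ICC 0.15, where unadjusted power is only 66–68%, the gain matters more. Chance imbalance has an SD of about 5.0 points if 85% of those tested are suppressed. The 6.7-point figure applies only if the proportion is 64%, which the protocol derives as a composite with retention. The power figures keep the SAP's 64% vs 82%. The change is worth making because it costs little, but the trial's conclusions do not depend on it.

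**What to change.** In SAP 3.5.2, prespecify two fixed covariates for all participants, outside the significance rule:

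- the participant's last VL status from a result strictly before the outcome window opens, within a stated look-back period, at the SAP's 1,000 copies/mL threshold, in three categories (suppressed, unsuppressed, none on record);
- the clinic's baseline proportion unsuppressed, computed from the same results.

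State that a VL dated on the enrollment day counts once, as baseline and not as outcome, and align the Table 1 window with the wording of 3.5.2. Without this, one result could sit on both sides of the model. Add baseline VL to Table 3, including the number with none on record. Keep the unadjusted model as supportive.

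The cost is SAP wording, a look-back rule to define, one clinic-level degree of freedom, and some old or missing baseline results that will weaken the covariate. No new data collection is needed.

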4.3 JUSTIFICATION FOR INTERVENTION

The intervention will be delivered by HCW during routine clinical visits; and works at improving clinic level effectiveness in care management. We anticipate at least 50 adolescents per site will be exposed to the intervention during the course of the study period. The intervention will be offered during regular clinic visits that are typically scheduled 1-6 monthly.

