6 STUDY INTERVENTION(S) OR EXPERIMENTAL MANIPULATION(S)

6.1 STUDY INTERVENTION(S) OR EXPERIMENTAL MANIPULATION(S) ADMINISTRATION

6.1.1 STUDY INTERVENTION OR EXPERIMENTAL MANIPULATION DESCRIPTION

The Data-informed Stepped Care (DiSC) intervention is comprised of a system to assign ALHIV to different levels of care, or “steps”, depending on their current and anticipated health care needs. Stepped care is a model grounded in Stages of Change Theory and has been used in mental health fields to organize provision of services, and to support clients, HCWs, and caregivers to identify interventions tailored to individual need. HCWs at participating sites will assign ALHIV to different levels or intensity of HIV services. The trajectory of services moves from a relative position of ALHIV autonomy to more intensive service provision. Intervention steps could start with multi-month refills or community treatment delivery, then social support activities (support groups, life skills activities), progress to individualized services (text messaging, ‘big brother/sister’ older peer support, motivational interviewing), and ultimately a case management approach involving referrals to specialized care like mental health or gender-based violence services, individualized counseling, and active tracking of individual participation in support and care services. The stepped care framework is designed to be flexible, to accommodate variable

Adapted from NIH Behavioral and Social Intervention Clinical Trial Protocol Template v3.0 - 20180827

individual and social support services available at each facility. A sample of potential intervention steps is presented below:

Sample intervention steps

Levels	Criteria for eligibility	Regular care	Additional HCW provided	Additional clinic recommended
Stepped down care	Meets MoH criteria except age	-Differentiated care	None	-Support groups (optional)
Not retained	At risk for loss	-3 monthly visits	-Pre-clinic reminders (text) -Individual peer support -3 monthly adherence counseling	-Support group
Viral failure	At risk for viral failure OR VL under 1000 but detectable	-Monthly visits (6 weekly for school going)	-Monthly adherence counseling -Motivational interviewing (one round of several sessions) OR Coaching -Individualized ART pick-up strategies	-Support group -Caregiver or support person DOTS

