Failed	Unsuppressed at last measure	-Monthly visits (6 weekly for school going)	-2 weekly adherence sessions (could make some on phone) -Accelerated repeat test timeline (3 month) -Prompt switch after second test -Case manager -DOTS by HCW (or caregiver/family)	-Support group -Special treatment failure support groups -Home visit by HCW -Viremia clinics

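### Scoring adherence interval by interval at 80% ties the result to refill length, so if DiSC shifts the refill mix the adherence rate ratio partly reflects visit spacing

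*SAP*

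**What the plan says.** SAP 3.5.4 defines the measure as a ratio: "Adherence will be evaluated using the proportion of days of pill dosing over days of inter-visit interval". It sets the cut ("A proportion over 80% as good adherence") and the unit of scoring ("The level of adherence during the past inter-visit interval will be assessed at each visit"). SAP Table 1 gives the same indicator: "Pill coverage estimated by days of dosing and inter-visit interval since last visit >80" (per cent), built from the visit date, the next visit date and the duration dispensed. The comparison is: "The dichotomized adherence will be compared between arms using mixed-effects Poisson regression with random effects for facility and participant and robust standard errors". Table 5 reports the number and percentage of intervals scored good.

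The SAP does not mention carrying surplus pills forward, coverage over the full 12 months, or refill length. The footnote to Table 5 allows adjustment only for enrollment factors that differ significantly between arms.

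On spacing, Protocol 4.3 says: "The intervention will be offered during regular clinic visits that are typically scheduled 1-6 monthly". Protocol 4.1 describes control visits as usually one to three months apart, whatever the adolescent's needs. Protocol 6.1.1 says of DiSC: "Intervention steps could start with multi-month refills or community treatment delivery". Its example table of steps also has monthly visits at the higher-need levels. SAP 3.5.3 counts a scheduled interval of three months or more as differentiated care and compares it between arms.

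**The concern.** A fixed proportion applied to intervals of different length allows different numbers of late days. Spacing also decides how many intervals an adolescent contributes: about 12 a year on monthly refills and 2 on six-monthly refills. Both features depend on something that happens after randomization and that the intervention is designed to influence. By making long scheduled intervals a secondary outcome, the SAP itself anticipates that the arms may differ in spacing.

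At stake is how the adherence rate ratio is read. Part of any difference between arms, or part of its absence, could come from how coverage is cut into intervals and not from how many days adolescents had pills in hand. This would affect adolescents who are fully observed. It is separate from the problem of intervals that never close.

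**Working it through.** The documents give no power calculation and no tolerance in days for adherence, so there is no figure of the plan's own to reproduce.

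**Inputs.** Ratio, strict 80% cut and per-interval scoring: SAP 3.5.4. Visits 1 to 6 months apart: Protocol 4.3. Control visits 1 to 3 months apart: Protocol 4.1. Assumption: days dispensed D equal the scheduled interval, with 1, 3 and 6 months taken as 30, 90 and 180 days. The documents never state a 180-day refill.

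**Step 1, tolerated lateness.** For L days late, the interval is good if D/(D + L) > 0.80, which means L < D/4.

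| Refill D | Last lateness scored good | First scored not good |
|---|---|---|
| 30 | 7 days: 30/37 = 81.1% | 8 days: 30/38 = 78.9% |
| 90 | 22 days: 90/112 = 80.4% | 23 days: 90/113 = 79.6% |
| 180 | 44 days: 180/224 = 80.4% | 45 days: 180/225 = 80.0%, not over 80% |

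**Step 2, same coverage over the year with one gap.** Take 360 dispensed days and a single gap of g days. There are m = 360/D intervals. The share good is (m − 1 + k)/m, where k is 1 if D/(D + g) > 0.80 and 0 otherwise. Days covered are 360/(360 + g).

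| Gap | Days covered | D = 30 (m = 12) | D = 90 (m = 4) | D = 180 (m = 2) |
|---|---|---|---|---|
| 20 | 360/380 = 94.7% | 30/50 fails: 11/12 = 92% | 90/110 = 81.8% passes: 100% | 180/200 = 90% passes: 100% |
| 30 | 360/390 = 92.3% | 30/60 fails: 11/12 = 92% | 90/120 = 75% fails: 3/4 = 75% | 180/210 = 85.7% passes: 100% |

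**Step 3, even lateness.** Six 30-day refills each 5 days late, and one 180-day refill 30 days late, both give 180/210 = 85.7%, and every interval is good. The dependence needs uneven lateness.

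**Step 4, direction.** Simulation of 200,000 people: 30-day gaps were drawn (a given chance of being late, exponential days late) and then pooled into 90- or 180-day refills, so pills and total gap are identical. The gap distributions are assumed.

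| Chance late, mean days | Days covered | % good at 30 / 90 / 180 | Ratio 180 to 30 |
|---|---|---|---|
| 0.3, 7 | 93% | 89.7 / 94.0 / 97.7 | 1.09 |
| 0.3, 14 | 88% | 82.5 / 79.2 / 81.9 | 0.99 |
| 0.3, 20 | 83% | 79.4 / 70.3 / 68.6 | 0.86 |
| 0.5, 20 | 75% | 65.7 / 50.8 / 42.9 | 0.65 |

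Longer refills are favored at high coverage and penalized at low coverage.

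**Step 5, size between arms.** Those ratios compare everyone on one refill length with everyone on another. Arms would differ less. Assume control is half on 30 and half on 90 days, and DiSC is 30% on 30, 30% on 90 and 40% on 180. Weight by 12, 4 and 2 intervals per person.

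- Equal coverage, 93% row: control (6 × 0.897 + 2 × 0.940)/8 = 0.908; DiSC (3.6 × 0.897 + 1.2 × 0.940 + 0.8 × 0.977)/5.6 = 0.918; ratio 1.01.
- Equal coverage, 75% row: control (6 × 0.657 + 2 × 0.508)/8 = 0.620; DiSC (3.6 × 0.657 + 1.2 × 0.508 + 0.8 × 0.429)/5.6 = 0.593; ratio 0.96.
- Same days late per visit instead (30% late, mean 7 to 20 days): ratio 1.01 to 1.03 with this mix, and about 0.99 if DiSC moves to 60% on 30 and 40% on 90 days. True coverage differs here too, so these ratios are not pure scoring effects.

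These are crude interval-weighted ratios, not estimates from the planned mixed model.

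**The case against.** The strongest reply is that nothing is defined differently by arm. There is one ratio and one cut, and two intervals with equal coverage always score the same. More permitted late days on a longer refill is what any proportion implies: 8 days late is 78.9% coverage on 30 days but 180/188 = 95.7% on 180, which is not equal adherence. All of this stands. A reader might infer that the definition of good adherence moves with the treatment arm; the SAP does not support that. What remains is narrower: equal coverage over a fixed period can score differently when lateness is uneven and refill lengths differ.

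It is also fair that the step table is only an example, that it gives visit frequencies and not days dispensed, and that no 180-day refill is stated. On the control arm's usual one to three months the tolerance runs from 7 to 22 days, still about threefold. Readers will see any shift in spacing, because Table 5 reports long intervals by arm. That shows the shift without removing it from the adherence result.

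Two further readings should be resisted. An adolescent can miss a visit under the primary outcome and still have good adherence, but these are different constructs and need not agree. The example step with "2 weekly adherence sessions (could make some on phone") could split a fully covered 30-day refill into 30/14 = 214% and 0/16 = 0%, but only if a session without dispensing is entered in the EMR as a visit, and the documents do not say that it is.

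**Conclusion.** The point holds in limited form. The adherence endpoint depends on refill length, through the tolerated lateness and through the number of intervals contributed, and refill length is a post-randomization variable that DiSC may change. The same 12-month coverage can score 92%, 75% or 100% in a simple case. Whether this biases the comparison depends on uneven lateness and on a refill mix that differs by arm. The direction is not fixed. The arm-level effect may be modest: 0.96 to 1.03 across the illustrative mixes, all resting on assumed gap patterns and mixes. It would go too far to say that no adherence effect could be read from the trial. For a secondary outcome this is a cheap improvement worth making, and it does not threaten the primary analysis.

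**What to change.** In SAP 3.5.4 and Table 5, add one value per participant: days covered by dispensed ART from enrollment to month 12, divided by days in that window. Carry stock forward, cap at 100%, and close the window at recorded death or transfer-out. Let a dispensing, not any visit, open a new interval. This fits the protocol, which counts adherence from the last refill (synopsis and 9.4.3) or the last dispensing date (outcome table in 8.1).

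Compare the mean proportion, and the proportion above 80%, between arms with clustering by facility. The participant random effect is no longer needed. Use this as the main adherence measure, or at minimum as a prespecified sensitivity analysis beside the per-interval result. Adjusting the per-interval model for refill length is not a clean substitute, because refill length may itself be affected by the intervention.

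The cost is SAP wording and an extra derivation from visit date and duration, both already listed in Table 1. There is one value per participant, so fewer data points. Adolescents who leave without a recorded transfer would accrue uncovered days, so the measure takes in some disengagement and silent transfer; the SAP should say so. Any dispensing outside clinic visits that the EMR does not capture would need a stated rule.
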